3.3 Exploratory Endpoints

Exploratory endpoints:

- At least 50% reduction in palpable splenomegaly from baseline per IWG criteria
- Red blood cell (RBC) transfusion during study drug treatment
- Change in quality of life from baseline as measured by the global health status/quality of life domain of the EORTC QLQ-C30
- Change in the summary score for the EORTC QLQ-C30 from baseline
- Progression-free survival (PFS) per IWG criteria
- Change in frequency of allelic mutations from baseline
- Change in EuroQol 5 Dimensions 5 Levels Health State Instrument (EQ-5D-5L) from baseline
- Change in fatigue-related symptoms from baseline as assessed by the PROMIS Fatigue 7a symptom items
- Change in impacts associated with fatigue from baseline as assessed by the PROMIS Fatigue 7a impact items.
- Translational biomarkers and correlation with clinical outcomes.
- Overall response of clinical improvement per IWG criteria
- At least 50% reduction in TSS at Week 24 from baseline (TSS_{50W24})
- Time to first TSS₅₀
- Duration of TSS₅₀
- TSS response rate at any time based on meaningful change threshold (MCT)
- Time to first TSS response
- Duration of TSS response

3.4 Safety Endpoints

The safety endpoints will be based on the following evaluations:

- Adverse event (AE) monitoring
- Physical examinations
- Vital sign measurements
- Electrocardiogram (ECG) variables
- Clinical laboratory testing (hematology and chemistry).

3.5 Pharmacokinetic Endpoints

Sparse PK samples will be collected at specified time points (see study activities table in [Appendix D](#)). Individual plasma concentrations of navitoclax and possible metabolite(s) from sparse PK sampling will be tabulated and summarized. Population PK parameters of navitoclax such as apparent oral clearance (CL/F) and apparent volume of distribution (V/F) may be estimated using non-linear mixed effects model.

Further details regarding PK sampling are provided in the Operations Manual, Section 3.7.

3.6 Biomarker Research Endpoints

Biospecimens (whole blood, plasma, bone marrow aspirate, and/or bone marrow core) will be collected at specified time points ([Appendix D](#)) throughout the study to evaluate known and/or novel disease-related or drug-related biomarkers in circulation or at tissue sites. Some of these samples may be optional. Types of biomarkers may include nucleic acids, proteins, lipids, and/or metabolites, either free or in association with particular cell types. The analyses may include but are not limited to: mutational status, BCL-2 family profiling, and inflammatory cytokine reduction. This research may be exploratory in nature and the results may not be included with the clinical study report.

Further details regarding the biomarker research rationale and collection time points are located in [Appendix D](#) and the Operations Manual, Section 3.8.

4 INVESTIGATIONAL PLAN

4.1 Overall Study Design and Plan

This is a Phase 3, double-blind, placebo-controlled, randomized, 2-arm study evaluating the efficacy and safety of the combination of navitoclax and ruxolitinib compared to ruxolitinib, in subjects with intermediate-2 or high-risk MF. The target population comprises adult subjects with MF who have not been previously treated with JAK2 inhibitor therapy with measurable splenomegaly and are not candidates for allogeneic-stem cell transplantation.

Approximately 230 subjects will be enrolled. Subjects will be randomized in a 1:1 ratio to one of the following treatment arms, with stratification factors of intermediate-2 versus high risk (Dynamic International Prognostic Scoring System Plus [DIPSS+])¹¹ and platelet count $\leq 200 \times 10^9/L$ versus $> 200 \times 10^9/L$:

- **Arm A – Experimental group:** navitoclax + ruxolitinib
- **Arm B – Control group:** placebo to match navitoclax + ruxolitinib

Dosing of study drugs:

- Navitoclax/placebo:
 - Platelet count $> 150 \times 10^9/L$: 200 mg once daily starting dose
 - Platelet count $\leq 150 \times 10^9/L$: 100 mg once daily starting dose; escalate to 200 mg once daily after ≥ 7 days, if tolerable (platelets $\geq 75 \times 10^9/L$).
 - After the Week 25 Day 1 visit, dose may be increased to 300 mg once daily at the discretion of the investigator based on platelet count for subjects with sub-optimal spleen response defined as failure to achieve a spleen volume reduction of at least 10%.
- Ruxolitinib (administered per USPI/SmPC/local prescribing guidance):
 - Platelet count $> 200 \times 10^9/L$: 20 mg twice daily starting dose
 - Platelet count $100 \times 10^9/L$ to $200 \times 10^9/L$: 15 mg twice daily starting dose.
 - Ruxolitinib dose adjustment in subjects with hepatic or renal impairment should be determined per local label/prescribing guidance.

Ruxolitinib and navitoclax/placebo will be administered beginning on Day 1 at the individualized starting dose based on baseline platelet counts determined within 24 hours prior to the first dose. The starting dose of ruxolitinib may be adjusted at the discretion of the investigator, as medically appropriate in consultation with the AbbVie Therapeutic Area Medical Director/Scientific Director (TA MD/SD), with subsequent increase in dose as described in [Table 1](#). Ruxolitinib and navitoclax/placebo dose reductions are permissible, as needed, for management of toxicities ([Section 6.2](#)).

[figure not shown]
Treatment with study drugs may continue until end of clinical benefit or occurrence of unacceptable toxicity or discontinuation criteria have been met. At the end of study drug treatment, a treatment completion and 30-day safety visit will be conducted.

After documented disease progression or initiation of post-treatment cancer therapy, the subject will enter the survival follow-up phase.

The schematic of the study is shown in [Figure 1](#). Further details regarding study procedures are located in the Operations Manual.

See [Section 5](#) for information regarding eligibility criteria.

Figure 1. Study Schema

DIPSS+ = Dynamic International Prognostic Scoring System Plus; Int = intermediate; Plt = platelet; PMF = primary myelofibrosis; SMF = secondary myelofibrosis

Option for Safety Lead-In Phase

The Sponsor plans to review safety data from at least 6 subjects administered navitoclax in combination with ruxolitinib for at least 8 weeks in either the frontline cohort of Study M16-109 or Study M16-191. If the review of safety data from Study M16-109 is not completed prior to dosing the 12th subject in Study M16-191, enrolment will be paused to complete independent data monitoring committee (IDMC) review of safety data from the first 12 subjects enrolled in Study M16-191.

4.2 Discussion of Study Design

Choice of Control Group

Ruxolitinib is the current standard treatment that is approved for patients with MF and induces improvement in splenomegaly and disease-related symptoms compared with placebo or best available therapy.² This study compares navitoclax in combination with ruxolitinib to placebo in combination with ruxolitinib. The choice of control group allows for a double-blind assessment of the contribution of navitoclax to the safety and efficacy of the backbone treatment of ruxolitinib.

Appropriateness of Measurements

Standard statistical, clinical, and laboratory procedures will be utilized in this study. All efficacy measurements in this study are standard for assessing disease activity in subjects with MF. All clinical and laboratory procedures in this study are standard and generally accepted.

Suitability of Subject Population

JAK2 inhibition induces down-regulation of the anti-apoptotic protein myeloid cell leukemia 1 (MCL-1) suggesting a role for navitoclax, a BCL-XL inhibitor, in the treatment of myeloproliferative neoplasms including MF. Therefore, subjects diagnosed with MF (PMF or SMF) represent the target population for this study.

Selection of Doses in the Study

The recommended starting dose of ruxolitinib for MF is according to the approved label and is based on the subject's baseline platelet count determined within 24 hours prior to the first dose: 20 mg twice daily ($> 200 \times 10^9/L$) or 15 mg twice daily ($100 \times 10^9/L$ to $200 \times 10^9/L$). The investigator may adjust the starting dose of ruxolitinib as medically appropriate after consultation with the AbbVie TA MD/SD, with subsequent increase in dose as shown in [Table 1](#).

As a BCL-X_L inhibitor, navitoclax causes thrombocytopenia via intravascular apoptosis of platelets. AbbVie internal data indicate that the effect of navitoclax on platelet reduction is exposure-related but may be diminished upon continued administration. Accordingly, thrombocytopenia may occur with navitoclax upon exposure to sufficient navitoclax concentrations. Additionally, thrombocytopenia and anemia are the primary reasons for ruxolitinib dose reductions.¹²

Preliminary data from Study M16-109 showed that weekly navitoclax dose escalation from 50 mg once daily to 300 mg once daily in combination with ruxolitinib at ≥ 10 mg, as was initially tested in Study M16-109, was generally safe without clinically relevant thrombocytopenia-related bleeding. In Study M16-109, 83% of subjects experienced a dose reduction of navitoclax during study treatment with the primary reason being thrombocytopenia. Of the subjects with navitoclax dose reductions for thrombocytopenia, 60% received 300 mg of navitoclax. Therefore, doses of navitoclax < 300 mg once daily seem to be better tolerated in patients with MF.

In addition, a mechanistic PK/PD model was used to evaluate the effect of navitoclax and ruxolitinib on platelets counts. The model incorporated different mechanisms by which navitoclax and ruxolitinib cause thrombocytopenia (navitoclax by peripheral platelet apoptosis and ruxolitinib by slowing platelet production). Simulations were conducted at:

- Different starting doses of navitoclax (100 to 300 mg once daily)
- Starting at 100 mg once daily with a weekly ramp-up to 200 mg once daily

Simulations indicate that the maximum decreases in platelet count and incidences of Grade 3/4 thrombocytopenia for the weekly ramp-up from 100 to 200 mg once daily were either similar to or slightly lower than those predicted at a flat starting dose of 200 mg (up to 5% difference).

The proposed starting dose of navitoclax in combination with ruxolitinib is 200 mg once daily or 100 mg once daily based on platelet counts determined pre-dose within 24 hours of first dose. To minimize the risk of relevant thrombocytopenia, AbbVie has proposed a lower starting dose of 100 mg once daily for subjects with a baseline platelet count $\leq 150 \times 10^9/L$. For subjects with a baseline platelet count of $\leq 150 \times 10^9/L$, the dose of navitoclax will be increased to 200 mg once daily after approximately 7 or more days, provided the platelet count remains $\geq 75 \times 10^9/L$. After the Week 25 Day 1 disease

assessment, navitoclax /placebo dose may be increased to 300 mg once daily at the discretion of the investigator based on platelet count for subjects with sub-optimal spleen response defined as failure to achieve a spleen volume reduction of at least 10%.

5 STUDY ACTIVITIES

5.1 Eligibility Criteria

Subjects must meet all of the following criteria in order to be included in the study. Anything other than a positive response to the questions below will result in exclusion from study participation.

Consent

- ✓ 1. Subjects must voluntarily sign and date an informed consent (or their legally authorized representative can sign and date the informed consent upon subject's understanding of the consent, if permitted by local regulations), approved by an independent ethics committee (IEC)/institutional review board (IRB) prior to the initiation of any screening or study-specific procedures.

Demographic and Laboratory Assessments

- ✓ 2. Subjects \geq 18 years of age.
- ✓ 3. Subject must be able to complete the MFSAF v4.0 on at least 4 out of the 7 days immediately preceding the date of randomization.
 - Subject has at least 2 symptoms with a score \geq 3 or a total score of \geq 12, as measured by the MFSAF v4.0.
- ✓ 4. Subject must meet the following laboratory criteria per local laboratory reference range at Screening:
 - Adequate bone marrow reserve; in the absence of growth factors, thrombopoietic factors, or platelet transfusions for at least 14 days prior to Week 1 Day 1.
 - Platelet count \geq $100 \times 10^9/L$
 - Absolute neutrophil count (ANC) \geq $1 \times 10^9/L$.
 - Renal function: calculated creatinine clearance \geq 30 mL/min by the Cockcroft-Gault formula.
 - Hepatic function and enzymes:
 - Aspartate aminotransferase (AST) and alanine aminotransferase (ALT) \leq $3.0 \times$ upper limit of normal (ULN)
 - Total bilirubin \leq $1.5 \times$ ULN (exception: subjects with Gilbert's Syndrome may have total bilirubin $>$ $1.5 \times$ ULN)
 - Coagulation: activated partial thromboplastin time (aPTT) and prothrombin time (PT) or international normalized ratio (INR) \leq $1.5 \times$ ULN.

- ✓ 5. Subject is willing and able to comply with procedures required in this protocol.

Disease Activity

- ✓ 6. Subject with a documented diagnosis of PMF as defined by the World Health Organization classification¹¹ or SMF (post polycythemia vera [PPV]-MF or post essential thrombocythemia [PET] – MF).
- ✓ 7. Subject classified as intermediate-2 or high-risk MF as defined by the DIPSS+ (Appendix F).¹³
- ✓ 8. Subject must not have received prior treatment with a JAK2 inhibitor.
- ✓ 9. Subject must not have received prior treatment with a B-cell lymphoma 2 homology 3 (BH3) mimetic compound or bromodomain and extra-terminal motif (BET) inhibitor or allogeneic stem cell transplant.
- ✓ 10. Subject has splenomegaly defined as spleen palpation measurement ≥ 5 cm below costal margin or spleen volume ≥ 450 cm³ as assessed centrally by MRI or CT scan.
- ✓ 11. Subject must be ineligible for stem cell transplantation at time of study entry due to age, comorbidities, or unfit for unrelated or unmatched donor transplant and other criteria per National Comprehensive Cancer Network guidelines.¹⁴
- ✓ 12. Subject must not have received splenic irradiation within 6 months prior to the Screening Visit or had a prior splenectomy.
- ✓ 13. Subject must not have leukemic transformation, defined as $> 10\%$ blasts in peripheral blood or bone marrow.
- ✓ 14. Subject with an Eastern Cooperative Oncology Group (ECOG) performance status of 0, 1, or 2.

Subject History

- ✓ 15. Subject must not have cardiovascular, endocrinologic, hepatic, immunologic, metabolic, neurologic, psychiatric, pulmonary, renal disease, or any other condition that, in the opinion of the investigator, could adversely affect the subject's participation in this study (including the capacity to provide consent) or the interpretation of study results.
- ✓ 16. Subject must not have history of an active malignancy other than MF within 2 years prior to Screening, except for:
 - Adequately treated in-situ carcinoma of the cervix
 - Adequately treated basal cell carcinoma or localized squamous cell carcinoma of the skin
 - Asymptomatic prostate cancer without known metastatic disease and with no requirement for therapy
 - Adequately treated in-situ carcinoma of esophagus or gastric mucosa.
- ✓ 17. Subject must not have known human immunodeficiency virus (HIV) infection. Note: HIV testing does not need to be conducted at Screening unless it is required per local guidelines or institutional standards.

- ✓ 18. Subject must not have known hepatitis B (HBV) or hepatitis C (HCV) infection requiring treatment. Subjects with an undetectable viral load within 3 months of Screening and those with serologic evidence of prior vaccination to HBV (i.e., HBs antigen [Ag-], and anti-HBs+) may participate. (Hepatitis B or C testing is not required at Screening unless it is required per local guidelines or institutional standards).
- ✓ 19. Subject must have a negative tuberculin skin test (purified protein derivative, PPD) and/or interferon-gamma release assay (IGRA), or any approved test per local guidelines, or have no evidence of latent tuberculosis (TB) prior to enrollment.
- ✓ 20. Subject must not have any clinically significant, uncontrolled medical conditions including, but not limited to:
 - Ongoing systemic infection (viral, bacterial, mycobacterial, or fungal)
 - Febrile neutropenia.
- ✓ 21. No history of an allergic reaction or significant sensitivity to constituents of the study drug (and its excipients) and/or other products in the same class.
- ✓ 22. No clinically relevant or significant ECG abnormalities, including ECG with QT interval corrected for heart rate (QTc) using Fridericia's formula (QTcF) > 450 msec (males) or > 470 msec (females).
- ✓ 23. No known active SARS-CoV-2 infection. Subjects must not have signs/symptoms associated with SARS-CoV-2 infection or known exposure to a confirmed case of SARS-CoV-2 infection during the 14 days prior to Screening.

Subjects who do not meet SARS-CoV-2 infection eligibility criteria must be screen failed and may only rescreen after they meet the following SARS-CoV-2 viral clearance criteria:

- Symptomatic subjects: At least 2 consecutive negative viral tests \geq 24 hours apart conducted at least 10 days after resolution of symptoms, defined as resolution of fever without use of antipyretics and improvement in respiratory symptoms (e.g., cough, shortness of breath).
- Asymptomatic subjects (if acceptable locally): At least 2 consecutive negative viral tests \geq 24 hours apart conducted at least 10 days after the prior positive result (Note: subjects who develop symptoms will follow guidance above for symptomatic subjects).

Frequency or timing of SARS-CoV-2 testing and the interval between testing for the above viral clearance criteria may be adjusted to account for epidemiological trends, updated information regarding infectivity, and local/institutional guidelines.

Contraception

- ✓ 24. For all females of child-bearing potential; a negative serum pregnancy test at the Screening Visit and a negative urine pregnancy test at baseline prior to the first dose of study drug.
- ✓ 25. Female subjects of childbearing potential must practice at least 1 protocol-specified method of birth control, that is effective from Study Day 1 through at least 30 days after the last dose of study drug. Female subjects of non-childbearing potential do not need to use birth control.

- ✓ 26. If female, not pregnant, breastfeeding, or considering becoming pregnant during the study or for approximately 30 days after the last dose of study drug.
- ✓ 27. If male, and subject is sexually active with female partner(s) of childbearing potential, he must agree, from Study Day 1 through 90 days after the last dose of study drug, to practice the protocol-specified contraception.
- ✓ 28. If male not considering fathering a child or donating sperm during the study or for approximately 90 days after the last dose of study drug.

Concomitant Medications

- ✓ 29. Subject must not receive anticancer therapy for another active malignancy or MF, including chemotherapy, radiation therapy, hormonal therapy (with the exception of hormones for thyroid conditions or estrogen replacement therapy) within 30 days, or hydroxyurea or other supportive medication used for cytoreduction, or steroid therapy for myelofibrosis or for anti-neoplastic intent within 7 days, prior to first dose of study drug, and during the study drug treatment period.
- ✓ 30. Subject must not receive medication that interferes with coagulation or platelet function within 3 days prior to the first dose of study drug or during the study drug treatment period, except for low dose aspirin (up to 100 mg daily) and low molecular weight heparin (LMWH).
- ✓ 31. Subject must not receive biologics for MF within 30 days prior to the first dose of study drug and during navitoclax and ruxolitinib administration.
- ✓ 32. Subject must not have received any live vaccine within 4 weeks prior to the first dose of study drug, or be expected to need of live vaccination during study participation including at least 4 weeks after the last dose of study drug.
- ✓ 33. Subject must not have been treated with any investigational drug within 30 days prior to the first dose of study drug, or currently be enrolled in another clinical study, or another research study except for observational studies with collection of demographic data.

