5.10 Randomization/Drug Assignment

Interactive Response Technology (IRT) will be utilized to register (screen and randomize) subjects on study. The site will contact the IRT to obtain a screening (subject) number only after the subject has signed the informed consent and prior to any study-specific procedures being performed (e.g., labs are drawn). Subjects who satisfy all eligibility criteria at Screening will proceed to being randomized based

on baseline platelet counts determined within 24 hours prior to the first dose. The site will contact the IRT to complete the randomization process and obtain study drug assignment.

The IRT will randomize subjects into 2 treatment arms using 1:1 randomization ratio. Randomization will be stratified by:

- Intermediate-2 versus high risk (DIPSS+)
- Platelet count $\leq 200 \times 10^9/L$ versus $> 200 \times 10^9/L$ (determined within 24 hours prior to first dose)

Blinding of Investigational Product

All AbbVie personnel with direct oversight of the conduct and management of the trial (with the exception of AbbVie Drug Supply Management Team), the investigator, study site personnel, and the subject will remain blinded to each subject's treatment throughout the study. To maintain the blind, the navitoclax film-coated tablets and placebo-film-coated tablets provided for the study will be identical in appearance.

The IRT will provide access to unblinded subject treatment information in the case of a medical emergency. AbbVie must then be notified within 24 hours of the blind being broken. The date and reason that the blind was broken must be recorded in the source documentation and electronic case report form (eCRF), as applicable.

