Navitoclax accelerates apoptosis of circulating mature platelets whether endogenous or transfused. This mechanism of toxicity differs from the thrombocytopenia caused by ruxolitinib and other conventional chemotherapy (i.e., toxicity to platelet progenitors in the bone marrow) and should, therefore, be managed according to the guidelines provided in [Table 1](#), unless previously discussed and approved with the AbbVie TA MD/SD.

Hematology samples must be collected within 24 hours prior to the first dose of study drug to determine dose of study drug, at 4 hours after the first dose of study treatment, and on Day 2 (see Activity Schedule, [Appendix D](#), and Operations Manual, Section 3.14). The investigator should consider additional hematology labs on Day 3 and/or Day 4 for subjects with a lower baseline platelet count and for subjects who experience a > 40% decrease in platelet count on Day 2 from the pre-dose platelet count. Additional hematology labs may be performed based on platelet counts as medically indicated at the investigator's discretion.

Any Grade ≥ 2 bleeding event (regardless of platelet count) will require interruption of dosing. Upon resolution of a Grade ≥ 2 bleeding event, study drug treatment may be reintroduced at the same or lower dose level (in consultation with the AbbVie TA MD/SD), provided the patient is asymptomatic with no evidence of an active bleeding.

If platelet transfusions are required in response to active bleeding, navitoclax/placebo dosing should be interrupted. It should be noted that platelet response with transfusions may not follow typical platelet kinetics of thrombocytopenia as with typical chemotherapy-induced thrombocytopenia. Procedures consistent with local institutional blood banking guidelines regarding platelet transfusions should be followed.

Platelet Transfusion Recommendations:

If platelet transfusion is deemed necessary, the treating physician should be aware that due to the rapid apoptotic effect of navitoclax on mature platelets, the increase in platelet counts post-transfusion may be lower and the duration of response may be shorter. Therefore, donor platelets collected as recently as possible prior to transfusion should be used. Additional transfusions may be necessary to achieve the desired platelet count. Post-transfusion platelet count monitoring should include:

- A platelet count obtained 10 to 60 minutes post transfusion.

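### The platelet and neutrophil floors are judged only at Screening: the mandatory pre-dose sample sets the dose but is not a start check, and no starting rule uses ANC

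*Protocol*

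**What the plan says.** All counts below are in 10^9/L.

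- **Entry floors.** Protocol 5.1, criterion 4, asks for platelets of at least 100 and ANC of at least 1. Its opening line fixes the time point: "Subject must meet the following laboratory criteria per local laboratory reference range at Screening". Only the 14-day interval free of growth factors, thrombopoietic factors and platelet transfusions is tied to Week 1 Day 1. Appendix D puts Screening at Day -28 to Day -1.
- **Route to randomisation.** Section 5.10: "Subjects who satisfy all eligibility criteria at Screening will proceed to being randomized based" on the platelet count from the 24 hours before first dose. That count also sets the platelet stratum.
- **Pre-dose sample.** Section 6.2: "Hematology samples must be collected within 24 hours prior to the first dose of study drug to determine dose of study drug". The next samples follow "at 4 hours after the first dose of study treatment, and on Day 2".
- **Navitoclax/placebo start.** Section 4.1 gives 200 mg above 150. At 150 or below it gives "100 mg once daily starting dose; escalate to 200 mg once daily after" at least 7 days if tolerated. Section 4.2 says the dose "will be increased to 200 mg once daily after approximately 7 or more days, provided the platelet count remains" at 75 or more. That bound governs the step up and not the start.
- **Ruxolitinib start.** Section 4.2: "The recommended starting dose of ruxolitinib for MF is according to the approved label", using the same 24-hour count. The lowest listed band is 100 to 200. Section 4.1 adds: "The starting dose of ruxolitinib may be adjusted at the discretion of the investigator", in consultation with the sponsor's medical or scientific director.

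**The concern.** The count that decides entry can be four weeks old on the day of the first dose. A fresh count is always available on that day, yet the protocol asks it only which dose to give.

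This matters because of the drug. Section 2.2 identifies thrombocytopenia as the toxicity that chiefly limits navitoclax dosing and lists neutropenia among the observed risks. The 4-hour and Day 2 samples show that an early platelet effect is expected, but both come after the first dose. A subject whose counts have fallen since Screening could therefore take a first dose at a count where the protocol would cut or stop the drug in someone already receiving it. Only Arm A would receive active navitoclax.

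Elsewhere the protocol anchors a criterion close to the start when it wants to. Criterion 24 repeats the pregnancy test before first dose, and criterion 3 ties symptom-form completion to the seven days before randomisation. The count floors have no such anchor.

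**Working it through.** No sample-size, power or alpha figure is involved, so this is a comparison of rules. Inputs: the starting tiers (4.1), the dose-adjustment rules (Table 1 and the step list in 6.2), and the schedule (Appendix D).

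**Step 1: age of the entry count.** Earliest Screening sample Day -28, first dose Day 1: a gap of at most 28 days. It can be as short as one day.

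**Step 2: search for a later check.** Sections 4.1, 4.2, 5.10 and 6.2 and Appendix D give the 24-hour sample two uses: choosing the dose and setting the platelet stratum. None re-applies a platelet or ANC floor to it.

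**Step 3: starting dose beside Table 1, navitoclax/placebo.**

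| Pre-dose platelets | Pre-dose ANC | First dose under 4.1 | Table 1, subject already on that dose |
|---|---|---|---|
| 75 to < 100 | >= 1.0 | 100 mg | stays at 100 mg; may rise after 7 days |
| 50 to < 75 | >= 1.0 | 100 mg | one level lower |
| < 50 | any | 100 mg | interrupt |
| <= 150 | < 1.0 | 100 mg | interrupt |
| > 150 | < 1.0 | 200 mg | interrupt |

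In the second row, one level below 100 mg is 75 mg by Table 1's list of levels, or 50 mg by the step list in 6.2.

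**Step 4: illustrative subjects (values assumed).**
- Screening platelets 190, ANC 1.1; pre-dose platelets 180, ANC 0.8. Criterion 4 and 5.10 are met, and the start is 200 mg. Table 1 interrupts at ANC 0.8.
- Screening platelets 105, ANC 1.5; pre-dose platelets 60, ANC 1.5. Criterion 4 and 5.10 are met, and the navitoclax/placebo start is 100 mg. Table 1 reduces at 60. No ruxolitinib band covers 60, so the site must turn to the label or the sponsor.

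**Step 5: length of exposure.** Navitoclax/placebo is taken once daily. If the site acts on the 4-hour or Day 2 sample, exposure is about one dose. How many subjects would be affected cannot be derived: the documents give no distribution of counts between Screening and Day 1.

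**The case against.** The best case for leaving the text alone has four parts.

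- **The Operations Manual.** The sentence requiring the pre-dose sample points to its Section 3.14, and a Day 1 go/no-go rule would naturally sit there. It is not among the public documents. This stands as a limit: the finding is about the protocol text available, and such a rule would reduce it to aligning 5.1 and 5.10.
- **Section 6.2 applies to everyone.** Its guidelines are for all subjects, so a sensible site seeing ANC 0.8 would hold the dose. That is likely. But Table 1 speaks of a current dose and of the dose before interruption, so it does not literally govern a first dose.
- **The ruxolitinib bands stop at 100.** This is a real partial floor for platelets. It does not reach ANC, and the starting-dose discretion in 4.1 is stated for ruxolitinib only.
- **Investigator judgement.** Criterion 15 leaves room for it, criterion 20 excludes febrile neutropenia and ongoing systemic infection, 5.5 allows interruption at any time for safety, and 6.2 allows further navitoclax/placebo modifications after sponsor discussion. All of these lower the risk. None sets a count below which the first dose is withheld.

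A reader might go further and infer that the starting rule contradicts Table 1. It does not, because one governs starts and the other governs doses already being taken. For the same reason, reading the second table row as a 1.33- to 2-fold overdose (100/75 to 100/50) is not supported.

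**Conclusion.** The point holds as a minor safety gap in wording. For ANC it is complete within the available text: no starting rule uses ANC, and a value below 1.0 leads to 100 or 200 mg where Table 1 interrupts. For platelets it is partial and is confined, for navitoclax/placebo, to counts below 75.

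A reader might also infer that the entry floor of 100 should be re-imposed on Day 1. The documents do not support that for navitoclax/placebo: at 75 to below 100, Table 1 keeps a subject at 100 mg, so the starting dose is not in conflict. The open question in that range is the ruxolitinib start.

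The conclusion assumes a literal reading of 4.1, 5.1 and 5.10 and no overriding rule in the Operations Manual. Frequency is unknown, and exposure is about one dose if the early samples are acted on. Power and type I error are unaffected.

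**What to change.** In 5.10 and in the 4.1 starting rule, add that the existing sample from the 24 hours before first dose must show ANC of at least 1.0 and platelets of at least 75 before randomisation and first dose. Add an IRT check and allow a repeat sample. At platelets of 75 to below 100, start only after consulting the sponsor's medical director, because no ruxolitinib starting band covers that range.

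The value 75 is the plan's own bound for the step to 200 mg and the lower edge of the Table 1 band in which 100 mg is maintained.

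No new sample is needed. Haematology and randomisation are both scheduled at Week 1 Day 1, and randomisation already uses the pre-dose platelet count. Failures would therefore fall before randomisation and leave the ITT population intact.

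The cost is a few delayed starts or late screen failures (number not computable). Some would be in subjects who have already stopped hydroxyurea or other cytoreduction for 7 days; the repeat sample limits this. The change also needs a protocol amendment, with ethics approval under 8.1 across about 190 sites in about 26 countries, so it is best carried with another amendment. It helps only subjects not yet started.
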